during face to face visits for drug screening or other purposes, following all COVID19 best practices including social distancing). During the screening interview, we will provide some information about how to use the tablets/ smart phones to access the surveys and take a picture of journal entries (for electronic administration, we will only provide this information to the treatment group). When will these measures be administered? Please see Table 2 “Schedule of Assessments” below for the timeframe indicating when these measures will be assessed. Please note we might make minor changes to the wording of the Qualtrics survey, for example, to improve the wording of some instructions to aid clarity or to correct typos and other small errors.

2. The study is being conducted in collaboration with our community partners for this study, NUWAY Inc. treatment center in Minneapolis, Minnesota. NUWAY has been providing substance use disorder treatment remotely via Zoom groups and individual sessions shortly after the COVID19 crisis began.

3.

4. NUWAY staff participate in many aspects of study implementation. NUWAY staff assist with recruitment, they will complete a pre-screening check list for each client referred to us, they provide us access to the treatment rooms and offices, they help us locate participants and prospective participants who have appointments with us, and they disseminate the iPads among other duties. For electronic administration, we will not use NUWAY treatment rooms or offices.

The counselors at the treatment center will review their caseloads and identify prospective participants who meet all the criteria on the check sheet (attached). Counselors will inform eligible clients of the opportunity to participate. Counselors will provide potential participants with study contact information and instruct them to reach out to study staff to ask questions and/or indicate their interest. If potential participants prefer, they may give permission for the counselor to share their contact information with study staff. Study staff will be responsible for final screening and obtaining consent from interested families. Study staff might also pre-screen participants using the counselor check sheet.

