To aid the treatment group in accessing the correct URL for uploading the photo of their journal and completing the Qualtrics questionnaire, the QR Code and the URL to the Qualtrics survey will be printed on a front page of the journal.

Please note, if any participant has technological difficulties with Zoom or with study procedures that we cannot adequately address during group sessions, we might place the participant with a research assistant in a Zoom break out room or make an appointment to meet with that participant by Zoom or telephone to help solve the difficulty.

See the table below for a summary of study activities by arm.

Study Activities by Arm

Baseline: All participants	Randomization	Phase 1. First 2.5 weeks	Phase 2. Following 2 weeks	Exit interview, immediately following Phase 2	Follow-up interview, approximately 1 month later
Screening and assessment battery All participants continue with treatment as usual at the host setting throughout this study	Control Group Treatment Group	Complete Qualtrics surveys 3-4 times a week, Earn gift cards This is the “group phase.” Attend approximately 8 hours of journaling groups. Complete Qualtrics surveys 3-4 times a week. Earn gift cards.	Complete Qualtrics surveys daily. Earn gift cards. This is the “independent practice phase.” Journal daily. Complete Qualtrics surveys daily. Earn gift cards.	Interview with research staff, Qualtrics survey. Interview with research staff, Qualtrics survey.	Interview with research staff, Qualtrics survey. After this interview, control group is mailed copy of journal with instructions for . Telephone interview with research staff, Qualtrics survey.

Detailed description of the activities of the treatment group. There are three phases to this intervention: the Group Phase (8 hours of content), the Independent Practice Phase (2 week duration after the group terminates in which participants practice PPJ 3-7 times per week), the Qualitative Exit Interview, which features the final quantitative Qualtrics questionnaire and an in-depth semi-structured exit interview to ascertain satisfaction with and criticism of PPJ, study logistics and the Follow-Up interview 30 days later which is a brief interview and final Qualtrics survey. We will encourage completion of the quantitative Qualtrics questionnaire before the exit interview facilitated by research staff for all research participants. Participants continue with treatment as usual during PPJ study activities.

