Please note we will thank NUWAY staff members by citing NUWAY and perhaps individual staff names in the acknowledgments section of academic presentations, posters, and manuscripts that result from these data. We may make periodic presentations to NUWAY staff about study observations and findings throughout the study period and afterward. When appropriate, we will offer CEUs for Social Workers to NUWAY staff for their attendance at these presentations and host inexpensive lunches or coffee hours for NUWAY staff (who are still working from the office during COVID19 at this time). When we are able, we will present NUWAY staff with honoraria as a gesture of thanks for their help with recruitment.

Data capture will also take place using REDCap. We will use REDCap to keep track of our screening procedures and study participation activities.

Measures. Sociodemographic factors will be assessed at the initial baseline measurement (e.g., age, sex, marital status, years of education, race/ethnicity, employment status, and annual household income). A variety of psychometric scales will be used at baseline and throughout the study. Please see Table 2 for the Schedule of Assessments and the text following after Table 2 for more detail about each assessment approach.

Contents of Qualtrics survey and REDCap survey are described herein in full.

Table 2. Schedule of Assessments.

PROTOCOL TITLE: Journaling and Addiction Recovery

VERSION DATE: 13 April 2021

	How long does it take to complete each of these measures	Baseline	At Every PPJ Qualtrics upload	Asked or Tallied after Group Phase Ends (Phase 1)	Asked or Tallied after Independent Practice Phase Ends (Phase 2)	Final Study Activities including 1 Month Follow-up
Baseline characteristics						
Sociodemographics, including current housing situation, i.e., "are you now living in sober living?"	3 minutes	X				
Hospital Anxiety and Depression Scale	3 minutes	X		X	X	X
10-item SIP-AD, addiction consequences	5 minutes	X				
Commitment to Sobriety (full scale)	2 minutes	X		X	X	X
Trait gratitude	2 minutes	X		X	X	X
AA Affiliation Scale	2 minutes	X				
Exposure to trauma	1 minute	X				
Using Medication Assisted Treatment	½ minute	X				
Legal issues: current involvement in civil legal case and current involvement in criminal court case	½ minute	X				
Satisfaction with treatment	2 minutes			X	X	X
Social Desirability Scale	4 minutes	X				

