Open ended questions: Experience with 10 th step, journaling, gratitude practices, and using a planner.	4 minutes	Verbally administered using REDCap			Verbally administered using REDCap	Verbally administered using REDCap
What have you already heard about the study?	1 minute	Verbally administered using REDCap				
Hypothesized Mediators						
Positive and Negative Affect Schedule, including three items comprising the serenity subscale	2 minutes	X	X	X	X	X
Abstinence Self Efficacy Question (single item)	1 minute	X	X	X	X	X
Commitment to Sobriety (single item)	2 minutes		X	X	X	X
Alcohol craving (single item)	½ minute	X	X	X	X	X
Drug craving (single item)	½ minute	X	X	X	X	X
Happiness with Recovery (single item)	½ minute	X	X	X	X	X

PROTOCOL TITLE: Journaling and Addiction Recovery

VERSION DATE: 13 April 2021

Individual items to assess specific impact of PPJ journaling practice ¹ (attached as "single items to assess change")	3 minutes	X	X	X	X	X
Satisfaction with Life	1 minute	X	X	X	X	X
Quality of life scale, modified to compare quality of life during recovery ("now") to quality of life during active addiction ("then") ¹	3 minutes	X	Global quality of life item only	X	X	X
Flourishing scale	2 minutes	X		X	X	X
Treatment Group Only						
# of Qualtrics surveys completed				X	X	X
Ease, helpfulness, satisfaction, effort of PPJ (for control group, ease, helpfulness, satisfaction, effort of filling out the survey questionnaires)	2 minutes		X	X	X	
# group sessions attended				X		
# homework assignments completed				X		
# journal entries completed				X	X	
Count of # of items entered into PPJ		X	X	X	X	
Eligibility rate and consent rate (treatment and control group)						X
On approximately the fourth session of group (halfway through the total # of sessions) ask: "what is working for me in this journaling group is...." And "what is not working for me in this journaling group is...."						
Open Ended Survey Question						
Treatment group: What are your thoughts about Positive Peer Journaling (PPJ) so far?	2 minutes			X	X	
Outcomes						
Recurrence of Substance Use				X	X	X
Treatment Retention at NUWAY (successfully exiting treatment with staff approval versus against staff advice or at staff request)				X	X	X
Qualitative Exit Interview	45 minutes					X
1 month follow up interview	25 minutes					X

Baseline characteristics.

- Sociodemographics

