6.1. Storage and Access: Quantitative data will be stored in a spreadsheet or data analytic software file and this data will be de-identified. Qualtrics will be used to collect data prior to download. Qualtrics is HIPAA compliant. Cases will be identified by code name or number only. Using a successful strategy we have used in the past, at baseline, participants will be asked to provide a "codename or number" that does not contain identifiers such as real name or birthday. Examples from the past have included "Rusty" or "007." An electronic key linking participants' real names with codenames/ numbers will be held on the PI's and research staffs' laptops in a password-protected file. This file will be deleted one year after the manuscripts based on this research are accepted for publication. Only the PI and research team will have access to the data. Codenames and real names are also listed on the "codename" sheet that individuals fill out at baseline when choosing their codename. These pages are kept in a locked file box or filing cabinet. We will also store certain kinds of data in University of Minnesota Box Secure Storage. Box Secure Storage is HIPAA compliant and is used for sharing confidential files. See <https://it.umn.edu/services-technologies/box-secure-storage>. We will use Box in two primary ways. First, we will

share research files with research team members whose computers cannot join VPN to access the secure drive. Second, we will use Box to share signed participant informed consent documents with the host treatment provider, NUWAY, if they would like to file these documents in their clients' treatment records. Other similar uses of Box Secure Storage might be employed for quantitative and qualitative data and other research files.

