7.1. Participants will be encouraged to email or call the PI in about a year's time to obtain study results in the form of academic posters or academic manuscripts or other products. Upon such requests, the PI will email or send via regular mail these products as well as an easy-to-understand fact sheet summarizing the results to date, to improve accessibility to study findings for lay readers. This opportunity is mentioned in the informed consent document. In general, the PI will share research findings at community-based, local, regional, and international conferences, during class or other lectures, and will publish study findings in academic journals. We will also make a presentation of findings to NUWAY staff when the study is over and throughout the study, as requested by NUWAY.

8. Study Duration

8.1.

- The duration for an individual participant's participation in the study is anticipated to be five to nine weeks as follows: Phase 1: 2.5 weeks, Phase 2: 2 weeks, a qualitative exit interview to take place as soon as possible at the 5 week mark, and a follow-up interview approximately 30 days after the exit interview.
- The duration anticipated to enroll all study participants: Enrollment will be rolling. We will recruit 10-20 individuals at a time to populate 1-2 treatment groups and corresponding individuals for the control groups. This study will last approximately 2 years. Typically, we will screen and consent and enroll participants during the week before groups start.
- The duration anticipated to complete all study procedures and data analysis: Including manuscript production and publication, approximately four years.

9. Study Population

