12.3. Identification of Potential Participants: See 12.1, above.

12.4. Recruitment Materials: Recruitment materials include the recruitment flyer, recruitment PowerPoint (if a presentation is made in client treatment groups), screening informed consent, and regular informed consent documents (copies are attached).

12.5. Payment to research participants: Payment will be made in the form of Target gift cards given out electronically. Target gift cards cannot be replaced if lost or stolen, this is stated on the regular consent form. Values of the Target gift cards will be based on participation as follows:

Participants will be compensated \$15 for the baseline assessment instrument and \$5 for attending each group session during the 3-week Group Phase (treatment group) or for completing 8 Qualtrics surveys (control group). Participants will be compensated \$5 each time they upload PPJ using Qualtrics in addition to the 8 group opportunities.

During the two-week Independent Practice Phase, participants are required to upload PPJ a minimum of 3 times per week but can upload a maximum of 7 times per week if they wish to but they will only be compensated up to 5 times (treatment group). During this same period, the control group will have equivalent opportunities to complete Qualtrics surveys. Each time they upload, they will be compensated \$5, assuming all aspects are completed (successful upload of photograph (for treatment group only) and answering study questionnaire items). Participants can feel free to upload more than 5 times a week (maximum would be daily) but would not be compensated for more than 5 times per week. Participants are not compensated additionally for uploads that take place during group sessions (treatment group individuals will already be compensated for attending group).

Participants will be compensated \$10 for the exit interview and \$10 for the 30 day follow up interview. Participants will be paid a \$20 bonus for completing the baseline interview, the exit interview, follow up interview, and at least 90% of all other study activities (group participation, homework, and the minimum number of independent PPJ uploads).

Total possible compensation including the bonus is \$160.

Payment to addiction treatment providers/administrators: We will offer \$40 in gift cards to treatment providers / administrators for reading, critiquing, and offering edits and comments to our draft PPJ treatment manual.

13. Withdrawal of Participants

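### Study findings may be presented to NUWAY staff while the trial is running, with no limit on content, although those staff judge the exits that score retention

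*Combined protocol and SAP*

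**What the plan says.** Section 5.2 (Data Capture) states: "We may make periodic presentations to NUWAY staff about study observations and findings throughout the study period and afterward". Section 7.1 adds: "We will also make a presentation of findings to NUWAY staff when the study is over and throughout the study, as requested by NUWAY". Under section 8.1 enrolment is rolling, in batches of 10-20, over a study of about 2 years. Presentations during the study would therefore overlap both recruitment and follow-up.

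Section 12.5 offers $40 "in gift cards to treatment providers / administrators for reading, critiquing, and offering edits and comments to our draft PPJ treatment manual". It does not name NUWAY, exclude anyone or give a time. Section 6.1 does use the term for NUWAY, in planning to "share signed participant informed consent documents with the host treatment provider, NUWAY".

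The audience for the presentations has several roles in the trial:

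- **Care of both arms.** The Study Activities by Arm table says: "All participants continue with treatment as usual at the host setting throughout this study".
- **Knowledge of arm.** Section 5.2 has counselors told of group attendance for one arm and of survey participation for the other.
- **Judgment of an outcome.** Table 2 defines retention as "successfully exiting treatment with staff approval versus against staff advice or at staff request". Sections 3.1 and 5.4 list retention as a primary outcome.
- **Reporting.** Under sections 5.2, 5.4 and 20.2, a NUWAY staff member reports retention and recurrence of use to the research team.

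No section restricts presentations to pooled or logistical content, or delays outcome results until follow-up ends. The one preventive step found is a reminder to treatment-arm participants in session 6 of Table 1. It is not addressed to staff.

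**The concern.** Whether an exit counts as approved is partly a judgment. It is made by staff who can tell which arm the client is in. If those staff also hear that journaling clients appear to be doing well, they may come to expect success in that arm and judge its exits more leniently. That would inflate the retention difference.

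A weaker route runs the other way. A counselor who has heard favourable results, or has read the manual, may offer gratitude or planning elements to control clients. That would dilute the difference.

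The two effects have opposite signs and could not be separated afterwards. Section 17.2 claims adequate power for retention, and section 17.3 plans to use the descriptive results to size a larger trial, so any distortion would carry forward.

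**Working it through.** **Inputs.** Section 17.2 gives retention of 96.6% versus 75.9%, N=76 and stated power of .82 (two-tailed, .05). Section 11.1 gives a current target of about 100. The documents do not state the allocation ratio, so I assume 1:1 (38 or 50 per arm). They give no contamination or relabelling rate, so those shares are also assumptions.

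**1. The plan's own figure.** Use the arcsine effect size h = 2·asin(√0.966) − 2·asin(√0.759), with power ≈ Φ(h·√(n/2) − 1.96). At n = 38 this gives 0.815, against the stated .82. The same method also reproduces the other three power figures in section 17.2: 0.942 (94%), 0.609 (.61) and 0.344 (.34). At n = 50 the retention power is 0.906.

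**2. Contamination.** Suppose a share c of controls takes on the full treated-arm rate. The difference becomes (1 − c) × (96.6 − 75.9) = (1 − c) × 20.7.

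| c | Control rate | Difference | Power, 38 per arm | Power, 50 per arm |
|---|---|---|---|---|
| 0 | 75.9% | 20.7 | 0.815 | 0.906 |
| 10% | 77.97% | 18.6 | 0.753 | 0.858 |
| 20% | 80.04% | 16.6 | 0.678 | 0.793 |

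**3. Relabelling.** Suppose a share b of non-approved exits in the journaling arm is recorded as approved. The spurious gain is b × (100 − true retention in that arm). With b = 10%:

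- At the section 17.2 treated rate: 0.10 × (100 − 96.6) = 0.10 × 3.4 = 0.34, about 0.3 points.
- With no true effect, so 75.9% in both arms: 0.10 × (100 − 75.9) = 0.10 × 24.1 = 2.41, about 2.4 points.

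**4. False-positive rate.** In the no-effect case, 10% relabelling moves the journaling arm to 78.3% against 75.9%. The chance of p < .05 rises from 0.05 to 0.057 at 38 per arm, or 0.059 at 50 per arm. It reaches 0.123 or 0.146 only if 30% are relabelled.

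**5. Which figures belong together.** At the section 17.2 rates, dilution costs 20.7 − 18.6 = 2.1 to 20.7 − 16.6 = 4.1 points, and relabelling adds 0.3. With no true effect there is nothing to dilute, and relabelling adds 2.4. The larger figure from each scenario should not be combined.

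**The case against.** The strongest reply is that staff exposure is already part of the design. Section 5.2 places a NUWAY staff member in all group sessions and has NUWAY or research staff practise the journaling, although section 14.1 makes attendance optional. Section 4.1 encourages participants to share goals with their counselors. Section 5.2 already reveals the arm. All of this stands. Restricting presentations would leave counselors aware of arm, possibly familiar with the journaling, and still judging exits. What it would prevent is the separate effect of outcome results on expectation.

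The illustrative rates are also open to challenge. A counselor passing on elements would hardly reproduce 8 hours of groups and two weeks of practice, so full-effect contamination is generous. Section 13.1 counts leaving without discussion and not returning as discontinuation, and such exits are hard to relabel. Section 5.2 asks both arms about journaling, gratitude, 10th-step and planner use, which measures contamination but does not prevent it.

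A reader might infer more than the documents support:

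- **That by-arm results will be shown.** The text allows findings without saying which. The main objective is feasibility, acceptability and logistics. The gap is the missing limit.
- **That the manual goes to NUWAY counselors.** Section 12.5 does not say so. It only fails to exclude them or set a date.
- **That referral is biased between arms.** Section 5.1 says "NUWAY staff assist with recruitment, they will complete a pre-screening check list for each client referred to us", but randomization follows screening and baseline. A change in who is referred would alter the sample in both arms alike, which bears on generalisability and not on the comparison.
- **That staff leniency distorts substance use.** Recurrence rests largely on urine and other drug screens, with self-report in addition. Leniency applies to exit approval.
- **That staff should receive no training in the journaling.** That would conflict with the staff role in group sessions described in section 5.2.

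**Conclusion.** The concern holds in a limited form, and its severity is minor. Two sections permit findings of any kind to reach staff who can infer the arm and who judge a primary outcome while the trial is still enrolling. The resulting expectation bias in retention is avoidable. Contamination through staff is a lesser addition, and the manual review is an unclosed gap.

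The size is unknown, and the worked figures show scale only. They rest on the section 17.2 rates and on assumed shares of 10-20% for contamination (full effect) and 10% for relabelling. The power and false-positive figures also assume 1:1 allocation. Relabelling at 10% is nearly harmless to the error rate. The protocol itself calls the study an underpowered pilot, so the reason to act is that the change is cheap, not that the harm is shown to be large.

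**What to change.** In sections 5.2 and 7.1, state that until the last participant's 1-month follow-up, presentations to NUWAY staff cover only recruitment, logistics and feasibility. No outcome or mediator results should be shown before then, whether by arm or for the journaling arm alone. In section 12.5, use manual reviewers with no caseload at the recruiting sites, or delay review by site staff until that date.

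This takes two or three sentences and needs no extra participants, staff or procedures. Site staff would hear results and review the manual later. Some goodwill could be lost at sites that supply recruitment, where section 12.1 reports 51% cancellations and no-shows for screening. The change does not remove the knowledge of the journaling and of arm that sections 4.1 and 5.2 already give to staff.
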